#### 3.4. Duration of Treatment

Subjects who meet eligibility criteria will be treated for at least 48 weeks during the blinded treatment phase. The maximum expected duration is approximately 214 weeks (includes the Screening period, blinded treatment period, the open-label extension phase and Follow-up period).

[figure not shown]
After Week 48, all subjects will continue to take their blinded study drug and attend visits every 12 weeks until the End of Blinded Treatment Visit. Once the last subject completes the Week 48 visit and Week 48 analysis is completed, all subjects will return to the clinic (preferably within 30 days) for an End of Blinded Treatment Visit. At the End of Blinded Treatment Visit, if safety and efficacy of B/F/TAF FDC is demonstrated following review of unblinded data, subjects in a country where B/F/TAF FDC is not available will be given the option to receive B/F/TAF FDC in an open-label (OL) extension phase for up to 96 weeks, or until the product becomes accessible to subjects through an access program, or until Gilead elects to discontinue the study in that country, whichever occurs first.

All subjects participating in the OL extension phase, without regard to their blinded treatment regimen, will return for study visits at Week 12 OL and every 12 weeks thereafter for up to 96 weeks.

[figure not shown]
Subjects who complete the study through the End of Blinded Treatment Visit and do not continue on the OL extension phase, will be required to return to the clinic 30 days after the End of Blinded Treatment Visit for a 30-Day Follow-Up Visit.

Treatment assignments will be provided to the investigators within 30 days of the last subject completing the End of Blinded Treatment Visit.

Figure 3-1. Study Schema

- a Following the Day 1 visit, subjects will be required to return for study visits at Weeks 4, 8, 12, and then every 12 weeks through the End of Blinded Treatment Visit. The Primary Endpoint will be met when the last enrolled subject completes the Week 48 visit.

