# 5.3. Dosage and Administration of B/F/TAF and DTG+F/TAF

Study drug B/F/TAF FDC, DTG, F/TAF FDC, and PTM tablets will be provided by Gilead.

**Treatment Group 1:** FDC B/F/TAF (50/200/25 mg) + PTM of DTG (50 mg) + PTM FDC of F/TAF (200/25 mg) administered orally, once daily, without regard to food (total of 3 tablets)

**Treatment Group 2:** DTG (50 mg) + FDC of F/TAF (200/25 mg) + PTM FDC B/F/TAF (50/200/25 mg) administered orally, once daily, without regard to food (total of 3 tablets)

After the End of Blinded Treatment Visit, all subjects who choose to participate in the open label extension will receive B/F/TAF FDC once daily for up to 96 weeks.

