#### 6.2. Pretreatment Assessments

### **6.2.1.** Screening Visit

Subjects will be screened within 30 days before Day 1 to determine eligibility for participation in the study. The following will be performed and documented at screening:

- Obtain written informed consent(s)
- Obtain medical history including history of HIV-1 disease-related events, and prior medications within 30 days of the screening visit
- If available, obtain documentation of historical genotype(s) (not required for entry to study)
- Complete physical examination (urogenital/anorectal exams will be performed at the discretion of the Investigator)
- 12-lead ECG performed supine
- Height
- Vital signs measurement (blood pressure, pulse, respiration rate, and temperature), including weight
- Obtain blood and urine samples as described in Sections 6.10.1 and 6.10.2
- Review concomitant medications
- Record any SAEs and all AEs related to protocol mandated procedures occurring after signing of the consent form

Subjects meeting all of the inclusion criteria, and none of the exclusion criteria, will return to the clinic within 30 days after screening for the Day 1 Visit into the study. Subjects must continue to take their prior treatment regimen up until their scheduled Day 1 visit.

From the time of obtaining informed consent through the first administration of study drug, record all SAEs, as well as any AEs related to protocol-mandated procedures on the adverse events eCRF. All other untoward medical occurrences observed during the screening period, including exacerbation or changes in medical history are to be captured on the medical history eCRF. See Section 7 Adverse Events and Toxicity Management for additional details.

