# 6.6.2. 30-Day Follow-Up Visit

Subjects who prematurely discontinue study drug during the blinded phase, and refuse to continue in the study through the End of Blinded Treatment Visit will be asked to return to the clinic 30 days after the completion of the Early Study Drug Discontinuation Visit, for the 30-Day Follow-Up Visit.

Subjects who complete the study drug through the End of Blinded Treatment Visit, and who do not wish to participate in the open-label extension, will be required to return to the clinic 30 days after the last dose of study drug, for the 30-Day Follow-Up Visit.

Those subjects who prematurely discontinue study drug during the blinded phase and continue in the study through at least one subsequent visit after the Early Study Drug Discontinuation Visit will not be required to complete the 30-Day Follow-Up Visit.

Subjects who prematurely discontinue study drug during the OL extension will be asked to return to the clinic 30 days after the completion of the Early Study Drug Discontinuation Visit, for the 30-day Follow-Up Visit. The subject will not continue attending the scheduled OL study visits.

Subjects who complete the OL extension phase will be asked to return to the clinic 30 days after the completion of study drug for the 30-day Follow-Up Visit.

For the purpose of scheduling a 30-Day Follow-Up Visit,  $a \pm 6$  days window may be used. The following evaluations are to be completed at the 30-Day Follow-Up Visit:

- Review of AEs and changes in concomitant medications
- Symptom-directed physical examination
- Vital signs measurement (blood pressure, pulse, respiration rate, and temperature), including weight
- Obtain blood and urine samples as described in Sections 6.10.1 and 6.10.2

At the 30-Day Follow-Up Visit, any evaluations showing abnormal results believed to be a reasonable possibility of a causal relationship with the study drugs will be repeated weekly (or as often as deemed prudent by the Investigator) until the abnormality is resolved, returns to baseline (Day 1) value, or is otherwise explained.

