# 1.1. Study Objectives

The primary objective of this study is:

• To evaluate the efficacy of switching from a regimen of dolutegravir (DTG) and emtricitabine (FTC; F) / tenofovir alafenamide (TAF) or DTG + FTC/tenofovir disoproxil fumarate (TDF) to a fixed dose combination (FDC) of bictegravir (B)/F/TAF versus DTG + F/TAF in virologically suppressed HIV-1 infected subjects with or without antiretroviral (ARV) resistance as determined by the proportion of subjects with HIV-1 RNA ≥ 50 copies/mL at Week 48

The secondary objective of this study is:

• To evaluate the safety and tolerability of the two treatment groups through Week 48

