#### **Study Periods / Phases**

Subjects will be treated for at least 48 weeks during the blinded treatment phase.

After Week 48, all subjects will continue to take their blinded study drug and attend visits every 12 weeks until the End of Blinded Treatment Visit. Once the last subject completes the Week 48 Visit and Week 48 analysis is completed, all subjects will return to the clinic (preferably within 30 days) for an End of Blinded Treatment Visit. At the End of Blinded Treatment Visit, if safety and efficacy of B/F/TAF FDC is demonstrated following review of unblinded data, subjects in a country where B/F/TAF FDC is not available will be given the option to receive B/F/TAF FDC in an open-label (OL) extension phase for up to 96 weeks, or until the product becomes accessible to subjects through an access program, or until Gilead Sciences elects to discontinue the study in that country, whichever occurs first.

All subjects participating in the OL extension phase, without regard to their blinded treatment regimen, will return for study visits at Week 12 OL and every 12 weeks thereafter for up to 96 weeks.

Subjects who complete the study through the End of Blinded Treatment Visit and do not continue on the open-label B/F/TAF FDC extension phase, will be required to return to the clinic 30 days after the End of Blinded Treatment Visit for a 30-Day Follow-Up Visit.

Treatment assignments will be provided to the investigators within 30 days of the last subject completing the End of Blinded Treatment Visit.

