# 3.2. Subject Grouping

For the randomized phase analyses using the All Randomized Analysis Set or the FAS, subjects will be grouped by the randomized treatment (labeled as B/F/TAF vs. DTG + F/TAF). For all other randomized phase analyses, subjects will be grouped by the actual treatment received. The actual treatment received will differ from the randomized treatment only when the actual treatment received differs from randomized treatment for the entire treatment duration.

For all B/F/TAF analyses, subjects will be grouped into the following 3 groups:

- B/F/TAF group: This group includes all subjects who actually received B/F/TAF in the randomized phase of this study, regardless whether subjects receive any B/F/TAF in the extension phase or not.
- DTG + F/TAF to B/F/TAF group: This group includes all subjects who actually received DTG + F/TAF regimen in the randomized phase of this study and then receive at least 1 dose of B/F/TAF in the extension phase
- All B/F/TAF group: This group includes all subjects who actually received at least 1 dose of B/F/TAF in either phase. This group includes the B/F/TAF group and the DTG + F/TAF to B/F/TAF group. Only data collected on and after the first dose date of B/F/TAF may be included.

Treatment comparisons will only be made between B/F/TAF and DTG + F/TAF for the randomized phase analysis.

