#### 7.1.6. Summaries of Adverse Events and Death

The number and percentage of subjects who experienced at least 1 TEAE will be provided and summarized by SOC, HLT, PT, and treatment group. For other AEs described below, summaries will be provided by SOC, PT, and treatment group. All AEs summary will use both the Safety Analysis Set for randomized phase analysis and All B/F/TAF Analysis Set for all B/F/TAF analysis, respectively.

- Any Grade 2, 3, or 4 treatment-emergent AEs
- Any Grade 3 or 4 treatment-emergent AEs
- All treatment-emergent study drug-related AEs

- Any Grade 2, 3, or 4 treatment-emergent study drug-related AEs
- Any Grade 3 or 4 treatment-emergent study drug-related AEs
- All treatment-emergent SAEs
- All treatment-emergent study drug-related SAEs
- All treatment-emergent AEs that caused premature discontinuation from study drug

A brief, high-level summary of AEs described above will be provided by treatment group and by the number and percentage of subjects who experienced the above AEs. Treatment-emergent deaths observed in the study will be also included in this summary.

Treatment-emergent death refers to deaths that occurred between the first dose date and the last dose date plus 30 days (inclusive).

Multiple events will be counted only once per subject in each summary. Adverse events will be summarized and listed first in alphabetic order of SOC and HLT within each SOC (if applicable), and then by PT in descending order of total frequency within each SOC. For summaries by severity grade, the most severe grade will be used for those AEs that occurred more than once in an individual subject during the study.

In addition to the above summary tables, all treatment-emergent AEs, Grade 3 or 4 treatment-emergent AEs, treatment-emergent study drug-related AEs, Grade 2, 3, or 4 treatment-emergent study drug-related AEs, and treatment-emergent SAEs will be summarized by PT only, in descending order of total frequency.

Summary of treatment-emergent AEs by SOC and PT will also be conducted for all subgroups listed in Section 3.4.2 for randomized phase analysis.

In addition, data listings will be provided for the following:

- All AEs
- Grade 3 and 4 AEs
- SAEs
- Study-Drug-Related SAEs
- Deaths report
- AEs leading to premature discontinuation of study drug

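### The All B/F/TAF cumulative event and graded laboratory tables give only crude percentages for groups with different B/F/TAF exposure; a rate per person-time should sit beside the event percentages

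*SAP*

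**What the plan says.** SAP 3.2 defines three columns for the All B/F/TAF analysis. The B/F/TAF group is everyone who received B/F/TAF in the randomized phase, whether or not they went on to the extension. The DTG + F/TAF to B/F/TAF group is those who crossed over in the extension. Of the third, pooled column it says: "This group includes the B/F/TAF group and the DTG + F/TAF to B/F/TAF group".

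The clocks differ. Under SAP 3.8.1, Study Day 1 is the first blinded dose for the B/F/TAF group and the first open-label dose for the crossover group. SAP 3.1.2.1 counts safety data for both until 30 days after the last B/F/TAF dose. The blinded phase has a floor but no stated ceiling ("Subjects will be treated for at least 48 weeks during the blinded treatment phase"). In the extension, subjects "will receive B/F/TAF FDC once daily for up to 96 weeks" (Protocol 5.3).

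The measure is the same throughout. SAP 7.1.6 states: "The number and percentage of subjects who experienced at least 1 TEAE will be provided and summarized by SOC, HLT, PT, and treatment group". The other adverse event categories there, the cardiovascular and hepatic events (7.1.7.2, 7.1.7.3) and the graded laboratory abnormalities (7.2.2.2) are likewise numbers and percentages of subjects. Kaplan-Meier methods are reserved for drug discontinuation (4.2.1). No person-time rate is planned in either document.

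**The concern.** A cumulative percentage rises with follow-up even when risk per unit time is constant. Two groups observed for different lengths of time can therefore show different percentages with no difference in risk, or similar percentages that hide one. The pooled column mixes the two durations in proportions fixed by extension uptake, so its percentage belongs to no single length of treatment.

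This table set describes what happens on B/F/TAF over the whole study. A reader will naturally compare its first two columns or quote the third as the incidence on B/F/TAF, and as planned the tables do not support either use.

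**Working it through.** **Inputs.** Total duration: "The maximum expected duration is approximately 214 weeks" (Protocol 3.4). Screening: "Subjects will be screened within 30 days before Day 1" (Protocol 6.2.1). Follow-up after the extension: 30 days (Protocol 6.6.2, "Subjects who complete the OL extension phase will be asked to return to the clinic 30 days after the completion of study drug"). Extension: at most 96 weeks. Minimum blinded treatment: 48 weeks.

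**Step 1: implied maximum blinded phase.** The 214 weeks can be decomposed but not independently reproduced, because the blinded maximum is not stated.

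214 − 96 − 30/7 − 30/7 = 109.4 weeks.

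**Step 2: per-subject maximum on B/F/TAF.**

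- B/F/TAF group: 109.4 + 96 = 205.4 weeks.
- Crossover group: 96 weeks.
- Ratio: 205.4 / 96 = 2.14. With the minimum blinded phase and a full extension: (48 + 96) / 96 = 1.50.

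**Step 3: ratio of group means.** Let B be blinded weeks, E extension weeks and f the share of the B/F/TAF group entering the extension. The ratio is (B + fE) / E. The documents do not give f or the realised B and E, so these are assumed values.

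| B | E | f = 0 | f = 0.25 | f = 0.5 | f = 1 |
|---|---|---|---|---|---|
| 109.4 | 96 | 1.14 | 1.39 | 1.64 | 2.14 |
| 60 | 96 | 0.625 | 0.875 | 1.125 | 1.625 |
| 84 | 48 | 1.75 | 2.00 | 2.25 | 2.75 |

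SAP Appendix 3 gives one indirect clue: 49 + 85 = 134 of 565 subjects (23.7%) were outside the US regions. If that share, and only that share, of the B/F/TAF group entered a 96-week extension, the ratio would be (109.4 + 0.237 × 96) / 96 = 1.38 with B = 109.4, and (60 + 0.237 × 96) / 96 = 0.86 with B = 60. The documents do not say which countries had extension access, so this is illustration only.

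**Step 4: effect on the percentage.** With the same constant first-event rate r in both groups, crude incidence is 1 − exp(−r × weeks × 7/365.25). At the maxima of Step 2:

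| Rate per 100 person-years | 96 weeks | 205.4 weeks | Ratio |
|---|---|---|---|
| 5 | 8.8% | 17.9% | 2.03 |
| 10 | 16.8% | 32.5% | 1.94 |
| 30 | 42.4% | 69.3% | 1.63 |

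At 5 per 100 person-years with no extension uptake, 109.4 versus 96 weeks gives 10.0% versus 8.8%, a negligible gap. With 60 blinded weeks and no uptake, 60 versus 96 weeks gives 1 − exp(−0.05 × 60 × 7/365.25) = 5.6% versus 8.8%, so the order reverses. Under the constant-rate assumption, an exposure-adjusted rate would show the same value in both columns in every one of these cases.

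**The case against.** The strongest reply is that these columns are descriptive. SAP 3.2 confines treatment comparisons to the randomized phase, and 7.1.7.2 and 7.1.7.3 repeat that no test is made in the All B/F/TAF analysis. Exposure is also reported: SAP 4.2.1 gives summary statistics and counts at thresholds to 168 weeks and beyond, by group. This stands as far as it goes: no formal inference is at risk, and an attentive reader can see that exposure differs. But a separate duration table does not let the reader recover first events per time at risk, and the pooled percentage is no easier to interpret for being untested.

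A reader might infer that the B/F/TAF column is inflated about twofold. The documents do not support that. The 2.14 is a per-subject ceiling derived from an approximate total. The extension is open only where B/F/TAF is unavailable, and it may end early. The group-mean ratio may be near 1 or below it.

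A reader might also infer that the secondary objective, "To evaluate the safety and tolerability of the two treatment groups through Week 48", gets no Week 48 safety result because the cumulative tables here run past Week 48. That does not follow either. SAP 2.2.1 says the Week 48 analysis was already conducted as the primary analysis, and SAP 2.3 limits this plan to the final analysis. Some safety output here is specific to Week 48: the fasting lipid sensitivity analysis (7.2.3) and the by-visit laboratory summaries (7.2.1). Both randomized arms share one follow-up rule, so the later cut-off is not in itself a source of bias between them.

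**Conclusion.** The point holds for the All B/F/TAF cumulative event and graded laboratory abnormality tables. They set side by side, and pool, crude percentages from groups with different B/F/TAF exposure, and nothing planned converts them to a common time scale. At the implied per-subject maxima of about 205 and 96 weeks, identical risk would appear as roughly a twofold difference for uncommon events and less for common ones. That size rests on maximum blinded time, a full extension for everyone and a constant event rate. The realised distortion cannot be stated from the documents, nor can its direction.

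This concerns how the final safety tables can be read. It does not touch the primary efficacy result or the randomized comparison, and it is a worthwhile, inexpensive improvement rather than a serious defect.

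**What to change.** In SAP 7.1.6 and 7.1.7, for the All B/F/TAF event summaries only, add beside each percentage the number of subjects with a first event per 100 person-years at risk on B/F/TAF. Time at risk starts at Study Day 1 of the All B/F/TAF analysis and stops at the first event or, without one, at the last B/F/TAF dose plus 30 days, matching the existing treatment-emergent window. Keep the percentages. The graded laboratory tables (7.2.2.2) can stay as percentages with a note pointing to the exposure summary.

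The cost is a few columns, since first and last dose dates are already defined in SAP 3.8.1. The rate carries the usual caveat: it summarises risk fairly only if the rate is roughly constant. If events cluster soon after the switch, longer follow-up dilutes the rate, and a footnote should say so. No Week 48 truncation of this plan's safety tables is needed.

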#### 3.3. Strata and Covariates

Randomization was stratified by prior NRTI backbone use (F/TAF vs. F/TDF) and documented or suspected history of NRTI resistance. For analysis, the baseline NRTI resistance stratum was re-classified based on virology data collected at both screening and/or baseline:

Baseline NRTI resistance stratum are as follows:

1) No NRTI mutation:

None of these following mutations/no NRTI resistance

2) K65R/E/N or  $\geq$  3 TAMs:

K65R/E/N or  $\geq$  3 TAMs that include M41L, L210W, or T69 insertions: K65R/E/N, or 3 or more thymidine analogue mutations (TAMs) that include M41L or L210W, or T69 insertions, (TAMs are: M41L, D67N, K70R, L210W, T215F/Y, and K219Q/E/R/N)

3) Any other pattern of NRTI mutation:

Any other pattern of NRTI resistance of M41L, D67N, K70R, L74I/V, Y115F, Q151M, M184I/V, L210W, T215F/Y, K219Q/E/R/N, T69D, K70E/G/M/Q/S/T, V75A/S/M/T

# 3.4. Examination of Subject Subgroups

Subject subgroup analysis will only be performed for randomized phase analysis unless specified below.

# 3.4.1. Subject Subgroups for Efficacy Analyses

The proportion of subjects with HIV-1 RNA < 50 copies/mL at Week 48 will be analyzed for the following subject subgroups (also see Section 6.1.2.2.2 for details):

- Age (years): (a)  $\leq 50$  and (b)  $\geq 50$
- Sex: (a) male and (b) female
- Race: (a) black and (b) nonblack
- Region: (a) US and (b) Ex-US
- Study drug adherence (%): (a)  $\leq$  95 and (b)  $\geq$  95 (based on adherence up to Week 48 Visit)
- Baseline NRTI resistance (determined based on virology data): (a) No NRTI mutation (b) any NRTI mutation
- Baseline NRTI resistance (determined based on virology data): (a) No NRTI mutation,
   (b) K65R/E/N or ≥ 3 TAMs (c) any other pattern of NRTI mutation
- Baseline M184I/V resistance (determined based on virology data): (a) No M184I/V mutation (b) any M184I/V mutation

The proportion of subjects with HBV Deoxyribonucleic Acid (DNA) < 29 IU/mL at baseline and Week 48 and the change from baseline in  $log_{10}$  HBV DNA by visit will be analyzed for the following subject subgroup:

• Subjects with HIV/HBV coinfection at baseline

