The duration of treatment at a dispensing period for a study drug is calculated as the minimum of (a) the last returned date of study drug at a dispensing period, (b) date of premature discontinuation of the study drug, and (c) next pill dispensing date of the study drug, minus dispensing date of the study drug.

The next pill dispensing date is the following dispensing date of the study drug regardless of the bottle return date.

For a record where the number of pills returned was missing (with "Yes" answered for "Was Bottle returned?" question), it is assumed the number of pills returned was zero. If the number of pills dispensed was missing or any study drug bottle was not returned or the bottle return status was unknown, then all records in that dispensing period for that study drug will be excluded from both denominator and numerator calculation.

Overall adherence will be calculated for both the randomized phase analysis and the all B/F/TAF analysis. For the randomized analysis, overall adherence will use all data from the entire dosing period up to the last dose date of the randomized study drug. For the all B/F/TAF analysis, overall adherence will use all available data collected from both randomized phase and OL phase for subjects who actually received B/F/TAF in the randomized phase, and data on or after the first dose date of extension B/F/TAF for subjects who actually received DTG + F/TAF in the randomized phase and received at least 1 dose of B/F/TAF in the extension phase.

Descriptive statistics for adherence to study drug regimen (n, mean, SD, median, Q1, Q3, minimum, and maximum) along with the number and percentage of subjects belonging to adherence categories (eg, < 80%,  $\ge 80\%$  to < 90%,  $\ge 90\%$  to < 95%,  $\ge 95\%$ ) will be provided by treatment group for subjects who return at least 1 bottle of randomized study drug, and who have calculable adherence for the randomized phase analysis and for All B/F/TAF analysis, respectively. No inferential statistics will be provided.

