The CMH analysis will be used to estimate the odds ratio and corresponding 95% CI for each region and overall. The homogeneity of the odds ratios across different regions will be tested using a Breslow-Day test and a corresponding p value will be reported.

6.1.2.2.2. Subgroup Analysis of the Proportion of Subjects with HIV-1 RNA < 50 copies/mL at Week 48 as Determined by US FDA-defined Snapshot Algorithm

Since the proportion of subjects with HIV-1 RNA  $\geq$  50 copies/mL at Week 48 as determined by the US FDA-defined snapshot algorithm (primary endpoint) is expected to be very low (around 2%), the efficacy analysis by subgroup will be conducted by assessing the proportion of subjects with HIV-1 RNA < 50 copies/mL determined by the US FDA-defined snapshot algorithm at Week 48 (a secondary efficacy endpoint) within each subgroup specified in Section 3.4.1 based on the FAS for randomized phase analysis.

For each level of subgroup factors, the proportion difference between treatment groups and the associated 2-sided 95% CIs will be computed based on an unconditional exact method using 2 inverted 1-sided tests.

Additionally, a logistic regression model will be performed which include subgroup, treatment, and treatment by subgroup interaction. The odds ratio and the associated 95% CI will be estimated within each subgroup. The homogeneity of the treatment effects between subgroups will be evaluated using a Wald test based on the interaction between treatment and the subgroup factor.

A forest plot of the treatment differences in HIV-1 RNA < 50 copies/mL (US FDA-defined snapshot algorithm) at Week 48 and their associated 95% CIs for each subgroup will be generated.

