   tables trtgrp*response/fisher; /*p value from Fisher's exact test*/
run;
```

f) Homogeneity test: Homogeneity Test of Treatment Effect (HIV-1 RNA < 50 copies/mL by US FDA-defined snapshot algorithm) Across Region in HIV-1 RNA < 50 copies/mL at Week 48 (Snapshot Algorithm). For each region, the odds ratio and its 95% CI are calculated from the CMH test. For overall, the odds ratio and its 95% CI are calculated based on the common odds ratio estimate from the CMH test. The p-value for the homogeneity test is based on the Breslow-Day test of the interaction between region and treatment group as follows.

```
proc freq data=xxx;
  tables region*trtgrp* response /all; /*p value from Breslow Day test,
  (trtgrp: 1, 2; response: 1: < 50, 2: >=50)*/
run;
```

g) Subgroup analyses for HIV-1 RNA < 50 copies/mL by US FDA-defined snapshot algorithm

For the subgroups of age, sex, race, baseline CD4 cell count, and study drug adherence, the proportion difference between two treatment groups and its 95% CIs are calculated based on an unconditional exact method using 2 inverted 1-sided tests, similarly to that for the primary efficacy endpoint.

- h) Homogeneity test: Homogeneity Test of Treatment Effect (HIV-1 RNA < 50 copies/mL by US FDA-defined snapshot algorithm) between Subgroups in HIV-1 RNA < 50 copies/mL at Week 48 (Snapshot Algorithm)
  - a. For the subgroups of age, sex, race, region and study drug adherence, the odds ratio and the associated 95% CIs are estimated for the response variable (response; coded as 1 for success and 0 for non-success) using a logistic regression model including subgroup factor (coded as 1 for the first subgroup and 2 for the second subgroup), treatment (trtgrp; coded as 1 for active [ie, B/F/TAF] and 2 for control), and treatment by subgroup factor.

```
eg. region stratum (region; coded as 1 for "US" and 2 for "Ex-US")
```

For example, for the age subgroup (agegrp; coded as 1 for < 50 and 2 for >= 50), the following SAS code will be used to generate the Odds Ratio and its 95% CI within the subgroup:

Note: For the following code, it is assumed that none of the variables have any formats applied to them. If they do, they must be removed before calling the code.

e.g. for the age subgroup, the following codes will be used to get Odds Ratio and 95% CI within subgroup:

```
proc genmod data=data descending; /*model for success*/
class trtgrpn agegrp;
model response = trtgrpn agegrp trtgrpn*agegrp/dist=bin
link=logit lrci;

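### On-treatment adherence up to Week 48 is analysed as an efficacy subgroup with between-arm inference, although it is observed after randomisation and is counted differently in the two arms

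*SAP*

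**What the plan says.** SAP 3.4.1 lists the subgroups for the proportion with HIV-1 RNA < 50 copies/mL at Week 48. Age, sex, race, region, baseline NRTI resistance and baseline M184I/V are all fixed before treatment. Study-drug adherence, divided at 95%, is not: it is "based on adherence up to Week 48 Visit".

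SAP 6.1.2.2.2 takes the FAS and applies one set of methods to the whole list:
- "For each level of subgroup factors, the proportion difference between treatment groups and the associated 2-sided 95% CIs will be computed", by the unconditional exact method;
- "a logistic regression model will be performed which include subgroup, treatment, and treatment by subgroup interaction", with an odds ratio in each subgroup;
- "The homogeneity of the treatment effects between subgroups will be evaluated using a Wald test" of the interaction;
- a forest plot of the differences.

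The inclusion of adherence is deliberate. Appendix 8 item 14g names it for the proportion difference, and item 14h says: "For the subgroups of age, sex, race, region and study drug adherence, the odds ratio and the associated 95% CIs are estimated".

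SAP 4.2.2 defines adherence from active-drug pill counts, summed over the drugs in the regimen. Treatment duration within a dispensing period is cut at premature discontinuation. A period with an unreturned bottle is removed for that drug. The adherence summary in that section is given "for subjects who return at least 1 bottle of randomized study drug, and who have calculable adherence", without inferential statistics. No section labels the adherence subgroup descriptive or says that its arm contrasts are non-randomised.

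**The concern.** A subgroup contrast inherits the protection of randomisation only if the subgroup is defined by something treatment cannot have changed. Pill-count adherence accrues over the same weeks that produce the Week 48 outcome, and tolerability of the assigned drug can affect how many doses are missed. Subjects in one adherence level may then differ between arms in ways that also predict virologic response. An arm difference or an interaction can appear with no drug difference, and a real one can be hidden.

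The classification is also not identical across arms. Both arms take three tablets daily, but the count rests on one active tablet for B/F/TAF and two for DTG+F/TAF.

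At stake is interpretation: the forest plot would show these rows, with an interaction p-value, beside valid baseline subgroups and with nothing to tell them apart.

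**Working it through.** The documents give no adherence rates and no figure for this subgroup, so there is no plan figure to reproduce. The numbers below use assumed inputs and show the mechanism only.

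**1. Exact example with no treatment effect in anyone.** Assume 15% of subjects are frail and respond at 80%, and 85% are not and respond at 96%. Low adherence occurs in 60% of frail subjects on arm A, 40% of frail subjects on arm B, and 20% of the rest on both. Response in a level = (frail share × 0.80 + other share × 0.96) / (frail share + other share).

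| | Arm A | Arm B | A − B | Odds ratio |
|---|---|---|---|---|
| Low | (0.09×0.80 + 0.17×0.96)/0.26 = 90.46% | (0.06×0.80 + 0.17×0.96)/0.23 = 91.83% | -1.36 points | 0.84 |
| High | (0.06×0.80 + 0.68×0.96)/0.74 = 94.70% | (0.09×0.80 + 0.68×0.96)/0.77 = 94.13% | +0.57 points | 1.11 |
| Overall | 93.6% | 93.6% | 0 | 1.00 |

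**2. The same example at the trial's size.** SAP 1.4 gives an actual N of 565; a split of 282/283 is assumed.
- Low level: about 73 and 65 subjects. SE = √(0.9046×0.0954/73.3 + 0.9183×0.0817/65.1) = 4.8 points, so the distortion is 1.36/4.8 = 0.28 SE.
- High level: about 209 and 218 subjects. SE = 2.2 points, so the distortion is 0.57/2.2 = 0.26 SE.
- Interaction: ln(1.115) − ln(0.844) = 0.278, with SE 0.736, so z = 0.38. The two-sided 5% Wald test then rejects in 6.7% of trials by normal theory and in about 5.3% by simulation.

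**3. Range under a second assumed mechanism.** A latent trait drives adherence (loading 0.7) and response (log-odds slope 0.5 to 1.0 per SD), and treatment has no effect on response. There were 4,000,000 simulated subjects per arm. Odds ratios are first arm versus second.

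| Share below 95%, by arm | OR, low level | OR, high level |
|---|---|---|
| 25% vs 25% | about 1.00 | about 1.00 |
| 20% vs 30% | 0.92 to 0.87 | 0.95 to 0.90 |
| 15% vs 35% | 0.84 to 0.74 | 0.90 to 0.79 |
| 30% vs 20% | 1.08 to 1.16 | 1.05 to 1.12 |

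The overall odds ratio is about 1.00 throughout. The distortion follows the arm imbalance in adherence and vanishes when there is none.

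**4. One active tablet against two.** Suppose everyone misses each tablet independently with probability 4% over 336 days. Falling below 95% needs at least 17 misses of 336 (one tablet) or at least 34 of 672 (two tablets). The probabilities are 19.4% and 9.9%, from identical behaviour. This is an extreme case. If miss rates vary between people (Beta(1.2, 40)), the shares are 18.7% and 17.7%; if tablets are always missed together, the gap is zero.

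**5. Who has a value.** Under SAP 4.2.2 pills after discontinuation are never counted as prescribed, so an early stopper can be scored as highly adherent. A subject with no evaluable dispensing period has no score. SAP 6.1.2.2.2 runs the subgroups on the FAS and does not say where such a subject goes.

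**The case against.** The strongest reply is that little hangs on this. Non-inferiority and superiority rest on the FAS snapshot interval for HIV-1 RNA ≥ 50 copies/mL (SAP 6.1.1.4). The adherence rows are one subgroup of a secondary endpoint, with no decision rule attached. Double-blinding with three tablets daily in both arms makes a large adherence imbalance less likely, and the example barely moves the interaction test's error rate. All of that stands, and it limits the severity.

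Four stronger readings are tempting but unsupported:
- A reader might infer that stopping drug lowers adherence and so loads drop-outs into the low level. The duration rule in SAP 4.2.2 prevents this.
- A reader might infer that early drop-outs in general leave both levels. The returned-bottle wording governs the descriptive summary in 4.2.2, not the subgroup analysis. Drug accountability is scheduled at each on-treatment visit from Week 4 and at the early discontinuation visit (protocol Appendix 2), so many drop-outs will have a value. Only those with no evaluable period lack one, and their number is not given.
- A reader might expect a false interaction finding to be likely. The assumed example does not show that; only larger assumed imbalances give larger distortions.
- A reader might see a contradiction with the statement in 4.2.2 that no inferential statistics are given. That statement concerns the adherence summary itself.

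It can also be argued that a footnote is enough, and that deleting a listed analysis after unblinded review harms transparency. The transparency point is right and shapes the fix. A footnote alone would still leave a non-randomised interaction p-value in the table.

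**Conclusion.** The point holds, at the level of a change that should be made but does not threaten the trial. The SAP attaches between-arm inference to a variable observed after randomisation and counted on different numbers of active tablets by arm, with no caveat, and it does not place subjects whose adherence cannot be calculated.

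The size depends wholly on unreported arm differences in adherence. In the main assumed example it is +0.57 points (high) and -1.36 points (low), each under a third of a standard error at N = 565. In the second mechanism the within-level odds ratios run from 0.74 to 1.16, and are about 1.00 when adherence is balanced. These figures illustrate the mechanism and do not estimate what happened in this trial. The primary non-inferiority test, its power and its alpha are unaffected.

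**What to change.** In SAP 3.4.1, 6.1.2.2.2 and Appendix 8 items 14g and 14h, remove adherence from the between-arm difference, odds ratio, interaction test and forest plot. In their place, tabulate HIV-1 RNA < 50 copies/mL by adherence category within each arm, with a 'not calculable' row so that the counts add up to the FAS. Label the table descriptive and non-randomised, and note that the count uses one active tablet for B/F/TAF and two for DTG+F/TAF.

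SAP 2.2.1 says the Week 48 analysis has been conducted, so record the change and its reason: in the SAP revision table if the SAP is still open, otherwise in the clinical study report, as SAP section 1 provides. Any adherence subgroup output already produced should stay on record and be labelled non-randomised in the report.

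The cost is some SAP text, one table shell and the loss of one customary forest-plot factor. Sample size, power and alpha do not change.
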